9.7 DATA ANALYSIS

Details of all analyses and variables specification will be defined in a separate SEAP.

Patients are grouped according the exposure to either Empagliflozin or DPP-4 inhibitors. Data will be analysed per group. Let the index period define the time from index date to the end of treatment as defined in [section 9.3.2](#) by current use, and the follow-up period the time from index date to the end of observation as defined in [section 9](#). Incidences will be derived if events of interest occur in the respective period. The main analysis will consider index periods only, a secondary analysis will consider only the time of the index period in the month of Ramadan in every year, while sensitivity analyses will consider respective follow-up periods, overall or during Ramadan only. Times from index date to first occurrence will also be determined per event of interest and described by means of Kaplan-Meier estimates and median times with 95% confidence intervals, where appropriate.

All individual data will be listed and described per group by means of summary tables presenting frequency counts and percentages for categorical data and arithmetic means, standard deviations, medians, minimum and maximum values for continuous data. Baseline is defined as the last observation on or before the index date.

For the assessment of the primary and secondary objectives, the main data analysis will be conducted in two stages:

- 1) Construction of the PS by modelling the exposure to Empagliflozin vs. DPP-4 inhibitor;
- 2) Estimation of the effect of exposure to Empagliflozin on the risk of ketoacidosis, severe urinary tract infections, volume depletion and dehydration compared to those exposed to DPP-4 inhibitor.

Propensity score stratification will be the primary method to control for the confounders in the analysis phase. The stratification will divide the study population in several groups (max. 5 groups) based on their propensity score value. Propensity score matching will also be used as secondary method in the analysis phase.

All statistical tests will be conducted with a two-sided significance level alpha of 0.05 and all analyses will be conducted using SAS statistical analysis software version 9.4 (SAS Institute, Inc., Cary, NC) or later.

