9.7.2 Main analysis using stratification

For the incident users of Empagliflozin along with their respective comparators, analysis will be performed using the “as-treated” (AT) approach. This corresponds to censoring individuals who discontinue use of the index drug, i.e. who either switch from the index drug to any other of the index drugs (Empagliflozin or DPP-4 inhibitor) during follow-up or who stop using the index drug. The AT approach is considering index periods.

For each event of interest, ketoacidosis, severe urinary tract infections, volume depletion, and dehydration, crude and adjusted incidence rates per cohort will be described and compared by means of incidence rate ratios (IRR). Incidence rates will be reported as point estimates and 95% confidence intervals (CIs). Crude incidence rates will be adjusted per 1,000 person-years. Per cohort and, where appropriate per stratum and/or subgroup, the number of person-years is the sum of length of index periods of all patients. Time to first event occurrence will be compared by means of hazard ratios and their 95% confidence intervals.

IRRs and hazard ratios are analysed using stratification. Strata are defined by PS quintiles. IRRs are investigated by means of a stratified Mantel-Haenszel analysis, while hazard ratios are investigated by means of a Cox regression, if proportional hazards can be assumed.

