4.4 General Principles

All individual collected and derived data will be listed and described per group by means of summary tables presenting frequency counts and percentages for categorical data and arithmetic means, standard deviations, medians, minimum and maximum values for continuous data.

All statistical tests will be conducted with a two-sided significance level alpha of 0.05 and all analyses will be conducted using SAS statistical analysis software version 9.4 (SAS Institute, Inc., Cary, NC) or later.

Baseline (Visit 1) is defined as the last observation on or before the index date.

Let the *index period* define the time from index date to the end of treatment with either EMPAGLIFLOZIN or DPP-4 inhibitor, and the *follow-up period* the time from index date to the end of observation. The *index period during Ramadan* and the *follow-up period during Ramadan*, respectively, are the subperiods of index and follow-up periods, respectively, that will fall in the months of Ramadan as defined in Table 2-1 above, where June 6th 2019 and May 25th 2020 are assumed as the end of Ramadan for the two study years.

Statistical Analysis Plan (SAP)

Document Date: 17APR2019

Document Version: 1.0 Final

Durations of periods, time spans between visits and other times since the index date will be individually derived in days.

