4.7.5 Ketoacidosis, severe UTI, depletion and dehydration

As main endpoints, ketoacidosis, severe UTI (namely pyelonephritis and urosepsis), volume depletion and dehydration, will be derived from corresponding AE reporting. Crude and treatment-adjusted incidence rates will be presented by group and period, together with incidence rate ratios of EMPAGLIFLOZIN relative to DPP-4 inhibitor, as point estimates and with 95% confidence limits. Treatment-adjusted incidence rates are defined as crude incidence rates per 1,000 person-years. Per group, and, where appropriate, per stratum and/or subgroup, the number of person-years is the sum of length of index periods of all respective patients.

For each endpoint, the time from index date to first occurrence in days is determined. If the endpoint does not occur for a patient, the time is right-censored by the duration of the respective period, index period or follow-up period. By group, times to first occurrence will be described by means of Kaplan-Meier estimates with 95% confidence limits and, where appropriate, median times with 95% confidence limits.

Crude and treatment-adjusted incidence rates and respective incidence rate ratios will be described in summary tables by group and period, and per period in subgroups by metformin status, GLD status and insulin status, respectively. Ratios are defined as Empagliflozin to DPP-4 inhibitors.

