4.9 Analyses

For descriptive analysis of parameters, see section 4.7 above. In the following, analysis of the endpoints is described in detail.

The effect of exposure to EMPAGLIFLOZIN on the risk of ketoacidosis, severe urinary tract infections, volume depletion and dehydration compared to those exposed to DPP-4 inhibitor will be estimated. Hence, the following is applied to each of the four outcomes of interest.

The endpoints will be analysed in the index period (primary), in the index period during Ramadan (secondary), in the follow-up period and in the follow-up period during Ramadan.

Estimation of propensity scores

In a preparatory step, for each patient, propensity scores (PS) will be estimated by means of logistic regression, estimating the likelihood of a patient receiving Empagliflozin based on prior and baseline confounders predictive of treatment. The statistical model will be built by a selection process optimizing the goodness of fit.

At first, the relationship between treatment (EMP, DPP-4 inhibitor) and all potential clinical confounder candidates will be tested in bivariate analyses. Based on the type of the candidate, Fisher's exact tests or Student's t-tests will be applied [Heiberger 2015]. In case of distributional constraints, χ^2 tests or Mann-Whitney U tests may be alternatively applied, respectively.

Clinically relevant confounder candidates include age, gender, body mass index (BMI), blood pressure, fasting blood glucose level at baseline, and baseline HbA1c, if available, comorbidity indicators like hypertension, dyslipidaemia, kidney diseases, kidney stones, history of kidney transplant, liver diseases, prostate diseases, pancreatitis, surgery, infections (other than UTIs) and heart diseases, if available, genital defects, urinary tract anatomical defects, laboratory measurements and relevant prior and concomitant medications at baseline. Relevant prior medications in the last 6 months and at baseline include insulin sulfonylureas, meglitinides, thiazolidinediones, α -glucosidase inhibitors, glucagon-like peptide-1 receptors, antihyperlipidemics (statins, fibrates, niacin), antihypertensive agents (diuretics, ACE inhibitors, beta blockers), antipsychotic medications, corticosteroids, tacrolimus, glucagon, interferon,

Statistical Analysis Plan (SAP)

Document Date: 17APR2019

Document Version: 1.0 Final

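### SAP 4.7.5 reports incidence rates for each period but gives one visible person-time rule, whole index periods; applied literally to Ramadan, absolute rates would come out about 11-fold too low

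*SAP*

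**What the plan says.** SAP 4.7.5 governs the four main safety outcomes. It states that "Crude and treatment-adjusted incidence rates will be presented by group and period", and defines the treatment-adjusted rate as the crude rate per 1,000 person-years. For the denominator it says that "the number of person-years is the sum of length of index periods of all respective patients".

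The periods are listed in SAP 4.9: the index period (primary), then "in the index period during Ramadan (secondary), in the follow-up period and in the follow-up period during Ramadan". SAP 4.4 makes the index period and the index period during Ramadan two separate terms. The Ramadan versions are each cut from the parent period by the dates in SAP Table 2-1, with the closing dates fixed by a further clause: "where June 6th 2019 and May 25th 2020 are assumed as the end of Ramadan for the two study years". The same section adds: "Durations of periods, time spans between visits and other times since the index date will be individually derived in days".

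Protocol 9.7.2, under the main as-treated analysis, has nearly the same denominator sentence: "the number of person-years is the sum of length of index periods of all patients". For Ramadan, the opening text of Protocol 9.7 says that "a secondary analysis will consider only the time of the index period in the month of Ramadan in every year".

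**The concern.** The person-years sentence sits in a section that covers all four periods but is built on the defined term for only one of them. The word respective in it qualifies the patients (by group, stratum or subgroup), not the period. The sentence appears to have been carried over from Protocol 9.7.2, where it is right, into a place where it also governs the Ramadan rates.

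The absolute Ramadan rate matters in its own right. Protocol section 7 records that the regulator asked for safety monitoring that includes Ramadan, and Protocol 8.2 makes the Ramadan period the exposure of the secondary objective. If Ramadan events are divided by a whole year of person-time, the result is falsely reassuring: Ramadan would look safer than the rest of the year even if it were not, and a count of zero would appear to exclude rates that the data cannot exclude.

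The outputs exposed are the eight Ramadan incidence tables per outcome (15.2, 15.4 and so on to 15.16, and their counterparts), which is 8 × 4 = 32 tables, plus Figures 2.2 and 2.4.

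**Working it through.** The documents state no Ramadan rate, Ramadan person-time or dilution factor, so there is no figure of theirs to reproduce. The check is person-time arithmetic.

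**Inputs from the documents**
- Follow-up of one year per patient (SAP 2.2); 750 patients per group (SAP 4.2).
- Ramadan dates in SAP Table 2-1: 5 May to 4 June 2019 and 23 April to 23 May 2020, 31 days each counted inclusively.
- SAP 4.4 end dates, 6 June 2019 and 25 May 2020: 33 days each from the Table 2-1 starts.
- Objective (Protocol 8.2, SAP 2.2): day 1 to day 29 of Ramadan, 29 days.
- First patient in Q3 2018, last patient in Q4 2019 (Protocol section 6).

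**Assumptions not in the documents**
- Uniform entry, with first patient on 1 July or 30 September 2018 and last patient on 1 October or 31 December 2019 (four windows).
- Exponential stopping of 0, 25 or 40% per year.
- 365 days at risk from the day after the index date.

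**1. Dilution of the absolute rate**

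Dilution = total index-period PY / index-period PY inside Ramadan.

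| Ramadan length | One patient, full year | Cohort, 4 windows × 3 stopping rates |
|---|---|---|
| 33 days | 365/33 = 11.06 | 10.74 to 11.11 |
| 31 days | 365/31 = 11.77 | 11.43 to 11.83 |
| 29 days | 365/29 = 12.59 | 12.22 to 12.64 |

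**2. What a group of 750 full-year patients would show (33 days)**

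Whole index period: 750 × 365/365.25 = 749.5 PY. Ramadan only: 750 × 33/365.25 = 67.8 PY.
- Zero Ramadan events: the exact two-sided 95% upper limit on the count is −ln(0.025) = 3.689. As written, 3.689/749.5 = 4.9 per 1,000 PY; correctly, 3.689/67.8 = 54.4 per 1,000 PY.
- Three Ramadan events: as written, 3/749.5 = 4.0 per 1,000 PY; correctly, 3/67.8 = 44.3 per 1,000 PY (unrounded PY).

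**3. The bound**

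Ramadan events are a subset of index-period events. Over one shared denominator, the displayed Ramadan rate cannot exceed the overall rate, and equals it only if every event falls in Ramadan. For a Ramadan window of d days and a Ramadan to non-Ramadan hazard ratio k, in full-year patients:
- displayed Ramadan/overall = kd / (365 − d + kd), always below 1;
- correct Ramadan/overall = 365k / (365 − d + kd).

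With d = 33:

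| k | Displayed | Correct |
|---|---|---|
| 1 | 33/365 = 0.09 | 1.00 |
| 3 | 99/431 = 0.23 | 1,095/431 = 2.54 |
| 10 | 330/662 = 0.50 | 3,650/662 = 5.51 |

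**4. Effect on the between-group rate ratio**

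The displayed ratio is the correct ratio times (Ramadan PY / total PY, empagliflozin) / (the same, DPP-4). With equal stopping the factor is 1.00. With 20% stopping in one group and 40% in the other it is 0.984 to 0.999, or the reciprocal (1.001 to 1.016), depending on which group stops more.

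**The case against.** The strongest reply is that the plan, read as a whole, already points to the right denominator. Protocol 9.7 limits the analysis to Ramadan time. SAP 4.4 defines the sub-period and derives period durations in days. SAP 4.9.2 says the secondary endpoints are handled like the primary ones, but in that sub-period. Substituting the sub-period into 4.7.5 gives Ramadan person-time, and a careful programmer may do just that. This stands, so the documents do not support the inference that the Ramadan rates *will* be 11-fold too low. They support only that the literal rule would make them so. It does not remove the defect, because the stated rule uses a defined term that excludes the Ramadan restriction, and the plan should not rely on a programmer setting it aside.

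Second, SAP 4.9.3 and part of 4.10 are not visible, and a period-specific rule could be there. That stands, and the point is limited to the visible text.

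Third, the only hypothesis tested (SAP 4.6) is empagliflozin against DPP-4 inhibitors. A reader might infer that this comparison is biased during Ramadan. It is not, to any material degree: both groups would be diluted by almost the same factor. The visible text plans no formal Ramadan-versus-overall test, so the harm lies in the absolute rates and in the comparison readers will make from them. Ramadan event counts are also tabulated, so an alert reader could question the rate, but would need the Ramadan person-time to correct it.

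Fourth, it is tempting to say that 29, 31 and 33 days are three rival definitions of Ramadan. Table 2-1 gives its dates with a tolerance of 1 to 2 days, and the SAP 4.4 end dates are the Table 2-1 end dates plus 2 days. Only the 29-day wording of the objective differs from that window.

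**Conclusion.** The point holds in conditional form. The visible person-time rule in SAP 4.7.5 is right for the main analysis and wrong, if followed as worded, for the Ramadan rates reported under the same section. It conflicts with the Ramadan rule in Protocol 9.7 and leaves unused the sub-periods of SAP 4.4.

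The dilution of absolute Ramadan rates would be 10.7 to 11.1 with the 33-day SAP 4.4 window and up to 12.6 with 29 days, given uniform entry between the milestone dates and up to 40% stopping per year. The bound at the overall rate needs no such assumptions. The between-group rate ratio moves by less than 2% in the scenarios checked.

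The same literal mismatch exists for the follow-up period outside Ramadan, but it is near zero if index and follow-up periods both end 30 days after supply.

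This should be fixed before analysis. Confidence is medium, because the rest of the plan points towards the correct reading and part of the SAP cannot be seen.

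**What to change.** In SAP 4.7.5, replace the person-years sentence with one that sums each patient's days in the respective period, naming all four: index, index during Ramadan, follow-up, and follow-up during Ramadan. Print that person-time beside every rate.

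Use one Ramadan window for counting both events and person-time. Reconcile the 29-day wording of the objective (Protocol 8.2, SAP 2.2) with the SAP 4.4 window, which runs from the Table 2-1 start dates to 6 June 2019 and 25 May 2020.

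The cost is SAP wording and modest programming. Period durations are already to be derived in days, so no new data are needed.

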4.7.6 Concomitant medication

Concomitant medications are defined as any medication other than Empagliflozin and DPP-4 inhibitors taken during the study. This includes any medication that started prior to enrollment,

Statistical Analysis Plan (SAP)

Document Date: 17APR2019

Document Version: 1.0 Final

but continued during the study, as well as medication that started after enrollment, but continued at the end of study.

Prior medications are defined as any reported medication that started prior to enrollment, whether stopped prior to enrollment or continued.

The prior and concomitant medications reported will be coded using WHO-DD in its 2020 version and summarized by ATC classes.

Frequencies of patients with at least one intake of prior medication, concomitant medication and concomitant medication at index date, respectively, will be presented in summary tables by ATC levels 1, 2 and 4.

4.7.7 HbA1c and Other Laboratory Tests

HbA1c will be described by summary tables per visit. Measured values in SI units as well as changes from baseline will be summarized if appropriate.

Other laboratory tests at baseline will be described by summary tables in SI units.

4.7.8 Completion Status and Discontinuation

A frequency table will describe the rate of subjects who completed or discontinued, and by reason of discontinuation. In a summary table, the length of follow-up period, i.e., the duration of observation, will be evaluated as continuous count of number of days and in categories of 1 to 30 days, 31 to 90 days, 91 to 180 days, 181 to 360 days and more than 360 days, respectively.

4.8 Handling of Missing Data

Data will be analyzed as reported. Missing data will not be replaced or imputed. Outlying values, if confirmed by site on data clarification, will be analyzed as reported.

Note that if specific endpoints (AEs i.e. ketoacidosis, volume depletion, dehydration serious UTI) are not reported for a patient in the AE section of the CRF it will be assumed that they did not experience that event.

Statistical Analysis Plan (SAP)

Document Date: 17APR2019

Document Version: 1.0 Final

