9. RESEARCH METHODS

This is a non-interventional study with new data collection.

This study will cover the period between Q3 2018 and Q4 2020. The main goals of this study are to examine the risk of ketoacidosis, severe urinary tract infections, volume depletion, and dehydration associated with the use of Empagliflozin compared to the use of DPP-4 inhibitors in T2DM patients. The study will use an “incident users” design and compare new users of Empagliflozin with new users of DPP-4 inhibitors. The index date will be defined as the date on which each identified new user receives the index prescription for Empagliflozin or DPP-4 inhibitors. The definition of drug exposure for Empagliflozin will be any patient using at least one prescription of Empagliflozin tablets (10 or 25 mg) or fixed-dose combinations with metformin. The comparator group will be comprised of patients with at least one prescription of a DPP-4 inhibitor: sitagliptin, saxagliptin, linagliptin, vildagliptin, alogliptin (and fixed-dose combinations of these drugs with metformin). Each member of the population exposed to Empagliflozin must have at least one prescription for Empagliflozin, with or without other Glucose-lowering Drugs (GLDs,) and no prior prescriptions of a DPP-4 inhibitor or Empagliflozin during the available pre-index period. Each member of the population exposed to a DPP-4 inhibitor must have at least one prescription for a DPP-4 inhibitor, with or without other GLDs, and no prior prescriptions of a DPP-4 inhibitor or Empagliflozin during the available pre-index period.

Follow-up will start the day after the index date and will continue until any of the following conditions are met: date of death or after 12 months of follow-up, or the date during follow-up that specific exclusion criteria are met, the date of the last continuous treatment of the index drug (Empagliflozin or DPP-4 inhibitor) plus a defined grace period (30 days after the end of the last prescription’s days’ supply in main analyses), or the date in which a new treatment episode starts with any of the other index drugs. Patients who discontinue an index drug and then subsequently initiate another index drug will not be allowed to re-enter the study. Patients will be followed-up for 12 months.

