9.2.2.5 Follow-up period

Follow-up will start the day after the index date and last until end of study data (date of death or date of study end), the date during follow-up when specific exclusion criteria are met, the end date of the treatment of the index drug (Empagliflozin or other SGLT2 inhibitor or DPP-4 inhibitor) plus a defined grace period (30 days after the end of the last prescription's supply in main analyses), or the date on which a new treatment episode starts with any of the other index drugs.

Patients with adverse events noted at the final follow-up visit or upon premature discontinuation of Empagliflozin or the comparator DPP-4 inhibitor will be monitored further until the resolution of those adverse events. Alternatively, those patients will be followed up until the PASS physician and sponsor agree that no further follow-up is necessary.

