9.9 LIMITATIONS OF THE RESEARCH METHODS

There are several methodological challenges when conducting epidemiologic studies to evaluate the association between glucose-lowering medications and outcomes of interest among patients with diabetes. These challenges include, but are not limited to, changes in treatment in response to advancing diabetes or due to adverse effects of specific drugs and time-varying risk of an outcome depending on duration of exposure

Another limitation is that, the number of patients may be low to assess the risk of DKA.

Some patients may discontinue the study before Ramadan period and will not contribute to the assessment of the safety during this period.

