3 STUDY OVERVIEW

The study will use an “incident users” design and compare new users of EMPAGLIFLOZIN with new users of DPP-4 inhibitors.

This study will be carried out by conducting successive surveys over the follow-up period. The investigator will be asked to record the information from the surveys in the case report forms

Statistical Analysis Plan (SAP)

Document Date: 17APR2019

Document Version: 1.0 Final

(e-CRFs) from each subject who was initially administered the drug following the study start date until the requested number of subjects is reached.

The index date for each identified new user is defined as the date on which they receive the index prescription for EMPAGLIFLOZIN or DPP-4 inhibitors.

Patients are enrolled if at least 18 years of age at the index date, diagnosed with T2DM in Saudi Arabia, and who have not used other SGLT2 inhibitors during the previous 12 months. Patients are not enrolled if they have known hypersensitivity to EMPAGLIFLOZIN, the comparator DPP-4 inhibitors or any of their excipients, if EMPAGLIFLOZIN or the comparator DPP-4 inhibitor is contraindicated according SFDA approved label, or if they are on prescribed fixed-dose combinations of SGLT2 inhibitors with DPP-4 inhibitors.

Follow-up will start the day after the index date and will continue until any of the following conditions are met:

- Death
- 12 months of follow-up
- specific exclusion criteria are met during follow-up
- the last continuous treatment of the index drug (EMPAGLIFLOZIN or DPP-4 inhibitor) plus a defined grace period (30 days after the end of the last prescription's days' supply in main analyses)
- a new treatment episode starts with any of the other index drugs.

Patients who discontinue an index drug and then subsequently initiate another index drug will not be allowed to re-enter the study.

Four study visits will be held, at baseline, after 16, 32 and 52 weeks of follow-up.

[figure not shown]
[REDACTED]

Statistical Analysis Plan (SAP)

Document Date: 17APR2019

Document Version: 1.0 Final

Figure 3-1: Study Visits

* from Visit 1

Table 3-1: Schedule of Visits

Assessment	Visit 1	Visit 2	Visit 3	Visit 4
Informed Consent	X			
Demographics	X			
Diagnosis	X			
Medical History	X			
HbA1c	X	*	*	*
Blood glucose level	*			
Other Laboratory/Renal Function	*			
Physical Examination (for vital signs)	X	*	*	*
Concomitant Medication incl. anti-hyperglycemic	X	#	#	#
Dose of Empagliflozin / DPP-4 inhibitor	X	#	#	#
Adverse Events		X	X	X

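### Person-time is not ended at last ascertainment for lost or withdrawn patients, and SAP 4.8 counts unreported primary outcomes as no event, so unobserved time can enter the primary rates as event-free

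*SAP*

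**What the plan says.** **Unreported outcomes.** SAP 4.8 states "Missing data will not be replaced or imputed" and adds that if the primary outcomes "are not reported for a patient in the AE section of the CRF it will be assumed that they did not experience that event".

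**When follow-up ends.** There are three lists.
- SAP 3: "Follow-up will start the day after the index date and will continue until any of the following conditions are met". Five conditions follow: death, 12 months, exclusion criteria met, last treatment plus a 30-day grace period after the end of supply, and start of another index drug.
- Protocol 9: "date of death or after 12 months of follow-up, or the date during follow-up that specific exclusion criteria are met", then the same treatment-related stops.
- Protocol 9.2.2.5: follow-up is to "last until end of study data (date of death or date of study end"), with the other stops much as before.

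None of the three names loss to follow-up, withdrawal of consent or a missed final visit.

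**Which window is primary.** SAP 4.9 analyses the endpoints primarily in the index period, and SAP 4.7.5 sums index periods to obtain person-years. SAP 4.4 lets the index period "define the time from index date to the end of treatment with either EMPAGLIFLOZIN or DPP-4 inhibitor". Protocol 9.7 ties the same period to current use in 9.3.2, which runs to the end of supply plus 30 days; SAP 4.4 does not repeat that. For patients without an event, SAP 4.7.5 says "the time is right-censored by the duration of the respective period".

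**Patients who leave early.** Protocol 9.9 says: "Some patients may discontinue the study before Ramadan period and will not contribute to the assessment of the safety during this period". SAP 4.7.8 tabulates discontinuation by reason.

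**The concern.** The outcomes come from adverse event reports gathered mainly at Visits 2, 3 and 4 (weeks 16, 32 and 52). A patient who stops attending while on drug was last recorded as continuing, so the case report form holds no last administration date, and SAP 4.8 rules out imputing one. The plan does not say where that patient's index period ends, yet an empty adverse event page is read as absence of the event.

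Person-time in which no event could be recorded goes into the denominator and lowers the rate. If loss is heavier on empagliflozin, the rate ratio falls too, which in a safety study is the direction that hides a signal. Loss could also be related to the outcome, for instance after an admission elsewhere, but the documents give no evidence on this either way.

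**Working it through.** **No planned figure to reproduce.** The 1,500 patients (750 per group) are attributed to SFDA requirements, with no event rate, power or dropout. The sizes below are illustrations.

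**Inputs from the documents.** One year of follow-up per patient; visits at weeks 16, 32 and 52; current use ends 30 days after supply ends.

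**Assumptions.** A fraction *f* of patients is lost; the event rate is constant; nothing else censors; events after loss never reach the case report form. Two loss patterns:
- *Uniform*: loss is spread evenly over the year, so a lost patient is observed for 0.5 year on average.
- *Visit*: the last visit is Visit 1, 2 or 3 with equal chance, so observed time averages (0 + 16 + 32)/3 = 16 of 52 weeks = 0.308 year, leaving 0.692 unobserved.

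Time counted after loss runs either to 12 months or to a limit of 60 or 120 days (an assumed 30 or 90 days of remaining supply plus the 30 days).

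**Formula.** Recorded rate / true rate = observed person-time / counted person-time.

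**Counted to 12 months, f = 20%.**
- Uniform: 1 − 0.20 × 0.5 = 0.900 (675.0 of 750 person-years observed), 10% too low.
- Visit: 1 − 0.20 × 0.692 = 0.862, 14% too low.

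**Limited by supply plus 30 days, f = 20%.**
- Uniform: 675.0/697.6 = 0.968 (60 days) and 675.0/716.2 = 0.942 (120 days), so 3% and 6% too low.
- Visit: observed time per patient is 0.80 + 0.20 × 0.308 = 0.8615 year. At least 20 weeks (140 days) remain after the last visit, so the limit always applies. 60 days adds 0.20 × 60/365 = 0.0329, giving 0.8615/0.8944 = 0.963. 120 days adds 0.0658, giving 0.8615/0.9273 = 0.929. These are 4% and 7% too low.

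**Rate ratio.** With equal loss in the same pattern the factors cancel. With 25% loss on empagliflozin and 10% on DPP-4 inhibitors, visit pattern, a true ratio of 1.00 would read:
- to 12 months: 0.827/0.931 = 0.89
- 120 days: (0.8269/0.9091)/(0.9308/0.9636) = 0.910/0.966 = 0.94
- 60 days: (0.8269/0.8680)/(0.9308/0.9472) = 0.953/0.983 = 0.97

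**Analyses without person-time.** SAP 4.9.1 analyses incidence within propensity score strata by logistic regression and states no person-time offset. SAP 4.7.4 divides by the whole Enrolled Set. A patient never seen after Visit 1 is a full non-event in both, and the supply limit does not help. For a rare outcome under the same assumptions, recorded risk / true one-year risk is the observed share, 0.900 or 0.862 at 20% loss.

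**The case against.** The strongest defence is that the plan already limits the damage. Protocol 9.7 with 9.3.2 ends the index period 30 days after supply runs out, and SAP 3 has the same stop. A lost patient has no further recorded prescription, so person-time should end there and not at week 52. This largely stands, and a reader should not infer that every lost patient is counted for a full year: no text says so. What remains is that SAP 4.4 omits the limit, the visit data and variable lists shown do not include days' supply, and even the limited time is unobserved.

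Second, SAP 4.4 ends the follow-up period at the end of observation, SAP 4.7.8 equates its length with duration of observation, and protocol 9.9 intends that early leavers do not contribute to Ramadan. So it would be wrong to infer that the plan never stops the clock for leavers. But the first two concern the follow-up period, which the protocol uses for sensitivity analyses, and the third is a statement of limitation, not a derivation rule.

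Third, events are not found only at visits. Patients are asked at Visit 1 to contact the physician about adverse events, all adverse events are collected from consent onward, and hospital data are documented for admissions with a study outcome. This stands and may shrink the effect. It still depends on the investigator hearing of the event, and the 24-hour duty for events of special interest in protocol Table 2 is stated for Jardiance only.

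Finally, treating no report as no event is ordinary for outcomes drawn from adverse event reporting. That is fair while the patient is under observation; the fault is the missing time limit.

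**Conclusion.** The gap is real and touches numerator and denominator of all four primary outcomes. The SAP does not end person-time at last ascertainment, does not say how end of treatment is dated for a patient lost on drug, and does not limit the no-event rule to observed time.

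The size is modest if the supply rule is applied: about 3–7% understatement at an assumed 20% loss, against 10–14% if time runs to 12 months. The logistic regression and the Enrolled Set percentages take the larger figure on either reading. A reader might conclude that the rates and the rate ratio are certainly biased. The documents do not support that: no loss rate is given, the rate ratio is unaffected by equal loss in the same pattern, and withdrawals with a recorded last administration date can be closed correctly.

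Parts of the SAP, including 4.9.3 and the end of 4.10, are not in the public text and could not be checked.

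**What to change.** 1. In SAP 3, 4.4 and 4.7.5, end the index and follow-up periods, and their Ramadan sub-periods, at the earliest of the existing stops and the last attended study visit, or a study-termination date at which adverse event status was checked.
2. Set that date the same way whether or not an event was reported. Using any documented contact would not do: a patient who calls about an event would gain both event and time, while an event-free patient who does not call would gain neither, which biases rates upward.
3. Limit the SAP 4.8 no-event assumption to time up to that date, and show events reported after it in a sensitivity analysis.
4. For incidence, use person-time in place of the logistic model as stated: the stratified Mantel-Haenszel rate ratio that protocol 9.7.2 plans and SAP 4.10 retains, or a rate model with a person-time offset.
5. Reconcile the SAP 4.4 index period with protocol 9.7 and 9.3.2.
6. Report loss and withdrawal by cohort, including patients with no visit after baseline.

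The cost is SAP wording and one date derived mainly from visit dates already collected. Person-years fall slightly, and a few late-reported events move from the primary to the sensitivity analysis.
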